Rational	
Optimal medication adherence (MA) is critical to treatment success and survival of patients with cancer. However, adherence rates to some anti-cancer regimens could be as low as 16% and often worsens overtime. Barriers to adherence are multi-faceted and require multi-dimensional interventions. Digital solutions can support complex interventions effectively and efficiently and are increasingly accepted by patients.
 
SAMSON is a novel patient-centred, comprehensive digital solution to improve MA in cancer. The solution consists of two synergistically operating elements:
 
 1. SAMSON mobile platform, including smartphone-based app to remotely prompt MA, monitor patient side-effects and deliver self-care advice; and computer-based app to enable adherence and side-effect reporting 2. Health professional tele-consultations, using motivational interviewing (MI) skills being trained via the motivational interviewing training platform (MITP) to promote patient's adherence and side-effect self-management. 
The SAMSON mobile app was tested on 30 people with haematological cancer at Peter Mac in 2021. The MITP was developed in 2022 and is being tested by healthcare professionals at Peter Mac.

Objectives	To evaluate the acceptability, feasibility (recruitment, randomisation, retention, intervention adherence and assessment processes) and potential efficacy of the SAMSON intervention solution among 30 to 50 patients with haematological, lung or melanoma cancer newly administered oral anti-cancer medicines.
Study design	
This is a pilot two-arm RCT. Recruitment will be undertaken over a period of six months and the intervention is expected to be completed in nine months from the recruitment commencement.
 
After completion of baseline questionnaires, participants will be randomised separately to either intervention or control groups (1:1 ratio), using a computer-generated randomisation chart. Participants in the intervention group will receive the SAMSON intervention solution, while those in the control group will receive usual care, for 12 weeks immediately following the randomisation.

Pilot Randomized Controlled Trial Study Protocol
Version 1.0 – 2 May 2023, Amendment 1 dated 26 June 2023

	
Primary outcomes, including:
 
 1. Acceptability (UTAUT) 2. Feasibility 
Secondary outcomes, including:
 
 1. Medication Adherence (MA) 2. Self-report adherence (ASK-12) 3. Toxicity self-management (PAM-SF) 4. Anxiety, depression and symptoms (PROMIS) 5. Quality of life (FACT-G) 6. Optimal intervention strategy 
See section 7.7 for more details on outcome assessments.
 
Data collection and results reporting will be in line with the Consolidated Standards of Reporting Trials (CONSORT) criteria for pilot RCTs (Schulz et al., 2010).

Number of participants	30-50 patients
Sample size	Sample size for this trial is pragmatic and based on both funds available and expected patient numbers in the study period.
Duration of individual's participation	16 weeks
Recruiting period	Approximately 6 months
Study duration and critical time-points	
The study will run for approximately ten months. Critical timepoints include:
 
 - Baseline (or study commencement) - Week 1 - Week 4 - Week 8 - Week 12 (intervention end) - Week 16 (endpoint assessment)
Intervention	
The intervention consists of two synergistically operating elements:
 
 - SAMSON mobile platform, including smartphone-based app to remotely prompt MA, monitor patient side-effects and deliver self-care advice; and computer-based app to enable adherence and side-effect reporting. - Health professional tele-consultations, using MI skills being trained via the MITP to promote patient's adherence and side-effect self-management by: 
 o Medication reconciliation, o MA education,

Pilot Randomized Controlled Trial Study Protocol
Version 1.0 – 2 May 2023, Amendment 1 dated 26 June 2023

	
 ○ Medication administration, missed dose and side-effect education, including side-effect management strategies, ○ Assessment of barriers and concerns ○ The structured counselling sessions will be either in person or online at baseline, week 1, 4, 8 and 12. The length of consultations will be tailored to each patient's need and adherence status, assessed by the healthcare professional who delivers the counselling sessions.
Usual care	
The usual care often includes:
 
 - An initial pharmacist consultation for medication reconciliation and medication dispensary consultation, contraindications, adverse drug reactions, administration instructions for each medication schedule, and address any patient concerns. - A consultation with the clinic clinician, to provide education about medication, and patient-focused management of side-effects. The clinic nurse will be the patient's ongoing contact for the management of any side-effects related to their treatment medication. - Telephone follow-up, provided by the oncology nurse, within 1-2-week time if no risk/need for earlier support is required. If the oncology nurse identifies there might be a need of extra support, the patient will be followed up with a telephone call within a few days. If a patient displays a high level of competence and no concerns during their education session, they will not be followed up. Instead, they will be asked to call or email the oncology nurse if required.
Measures	
Patient-reported outcome measures will be administered via REDCap, a secure online data collection tool, via email or in hard copies. All study measures administered are reliable and valid (see section 7.3 for more details).
 
Primary 1- Acceptability will be measured by a questionnaire, guided by the Unified Theory of Acceptance and Use of Technology (UTAUT) at week 12
 
Primary 2- Feasibility will be measured both quantitatively and qualitatively throughout the study, including recruitment, randomisation, retention, intervention adherence, and assessment processes. For intervention patients, responses to weekly side effects surveys and daily medication reminders will also be measured.
 
Secondary 1- Medication adherence will be measured by medication refill adherence (MRA) at week 16.
 
Secondary 2- Self-report adherence will be measured by ASK-12 at weeks 1 and 12
 
Secondary 3- Toxicity Self-management will be measured by the Patient Activation Measure-Short Form (PAM-SF) at weeks 1 and 12
 
Secondary 4- Anxiety, Depression and Symptoms will be measured by PROMIS scales at weeks 1 and 12

Pilot Randomized Controlled Trial Study Protocol
Version 1.0 – 2 May 2023, Amendment 1 dated 26 June 2023

	
Secondary 5- Quality of Life will be measured by the Functional Assessment of Cancer Therapy–General (FACT-G) at weeks 1 and 12.
 
Secondary 6- Optimal intervention strategy will be measure by qualitative questions in the UTAUT survey at week 12 to identify the optimal dose of delivering MI tele-consultations.
 
See section 7.7 for more details on outcome measurements and thresholds.

Data collection	
Data collection will be either in person or online.
 
Screening
 
All patients:
 
 • Participant Information Consent Form (PICF) • Demographics form 
Week 1 to 12
 
All patients:
 
 • Feasibility data 
Intervention patients:
 
 • Side effects monitoring • Self-responses to medication reminders 
Week 1 and 12
 
All patients:
 
 • ASK-12 • PAM-SF • PROMIS • FACT-G 
Week 12
 
Intervention patients:
 
 • UTAUT 
Week 16
 
All patients:
 
 • MA
Inclusion criteria	
 1) A confirmed diagnosis of any-stage haematological, lung or melanoma cancer; 2) Scheduled to commence oral anti-cancer medicine(s) as part of routine care or commencing treatment/currently treated with the medication for less than 12 months; 3) Willing to have oral anti-cancer medicine(s) dispensed at Peter Mac; 4) Over 18 years old; 5) Proficient in English; and 6) Accessibility to the internet, a smartphone (and computer), and/or telehealth.
Exclusion criteria	
 1) Too unwell to participate in the study as determined by the patient’s treatment team. 2) Remaining indication treatment period of oral medications for cancer therapy is less than 12 weeks.

Pilot Randomized Controlled Trial Study Protocol
Version 1.0 – 2 May 2023, Amendment 1 dated 26 June 2023

	3) Demonstrated cognitive or psychological difficulties that would preclude study participation as defined by the treatment team’s cognitive and/or psychiatric assessment or patient’s disclosed medical history.
Statistical considerations	
Quantitative data: Given the relatively small sample size, and that this is a feasibility and acceptability study, analysis of outcome data will be mainly descriptive (e.g. counts/ percentages, means/ standard deviations or medians/ inter-quartile ranges, etc.) These measures will be used to summarise the information in order to describe: 1/ sample demographics; 2/ participants’ acceptability and intention to use the SAMSON (performance expectancy, effort expectancy, social influence, facilitating conditions and behavioural intention), and 3/ patients’ adherence, side-effect monitoring, toxicity self-management, anxiety, depression and symptoms and quality of life. Between- and within-group comparisons on the outcomes of interest will be conducted, using chi squared t-tests and linear regression. Statistics and data software (STATA) version 17 (STATAcorp, 2021) will be used to analyse the quantitative data.
 
Qualitative data from the UTAUT questionnaire: will be analysed for themes in NVivo 12.
 
Results from this pilot RCT can be used to inform the design of a full RCT to evaluate the efficacy of SAMSON later.

Project timeline	
It is anticipated that the study will run for approximately 12 months. Key activities during the study timeline are:
 
January – February 2023 Protocol development Establish project team
 
March – May 2023 Acquire Peter Mac’s and Swinburne’s Ethics approvals Refine SAMSON app and MITP
 
June – November 2023 Participant recruitment
 
June 2023 – March 2024 Data collection
 
April - June 2024 Analyse data and prepare study report

Pilot Randomized Controlled Trial Study Protocol
Version 1.0 – 2 May 2023, Amendment 1 dated 26 June 2023

Study and assessment schedule

Protocol Activity	Baseline (study commencement)	Week 1	Week 4	Week 8	Week 12 (intervention end)	Week 16 (last data collection)	Will be done by
Inclusion/Exclusion criteria	x						RC (Referred by doctors/nurs/pharms)
Consent	x						Pts & RC
Demographics	x						Pts & RC
SAMSON app	x	x	x	x	x		Intervention pts & RC
Initial MI consultation: 
 Provide patient education on oral anti-cancer medicines. Identify past, present, and potential future barriers to MA. Resolve any barriers to MA, using MI techniques and document identified risks and barriers within the SAMSON web portal, for the next follow-up teleconsultation. 	x						Pharm & intervention pts
First MI teleconsultation 
 Check the participant's understanding of their diagnosis, current symptoms, self-care strategies and medication regimen, and how they are managing now. Explore what helps facilitate adherence for the individual patient, and any barriers to treatment adherence. Use MI techniques to assist the patient to identify reasons why adherence is important for them and to develop problem-solving strategies to combat identified barriers. Once strategies have been identified, guide the patient toward action and assist with self-care strategy rehearsal. Provide evidence-based information/resources and remind patients 		x					Nurs/Pharm & intervention pts

Pilot Randomized Controlled Trial Study Protocol
Version 1.0 – 2 May 2023, Amendment 1 dated 26 June 2023

Protocol Activity	Baseline (study commencement)	Week 1	Week 4	Week 8	Week 12 (intervention end)	Week 16 (last data collection)	Will be done by	
the SAMSON app provides self-care strategies for relevant side-effects.								
Follow-up MI teleconsultations 
 Review adherence rates and symptom survey and any issues from the previous teleconsultation. Assess adherence to oral anti-cancer medication. Explore barriers to treatment adherence. Discuss benefits and coach re adherence. Discuss symptoms / side effects. Coaching re evidence-based self-care strategies. Summarise the session + assess understanding. Discuss follow-up consultations – check convenient time. Complete checklist + patient summary. 			x	x			Nurs/Pharm & intervention pts	
Final MI teleconsultation 
 Review adherence rates and symptom survey and any issues from the previous session. Assess adherence to oral anti-cancer medication. Explore barriers to treatment adherence. Discuss benefits and coach re adherence. Discuss symptoms / side effects. Guidance re evidence-based self-care strategies. Summarise the session + assess understanding. Discuss support network and self-management. Discuss final session Complete checklist + patient summary. 					x		Nurs/Pharm & intervention pts	
Outcomes measurements								
Acceptability (UTAUT)					x		Intervention pts	

Pilot Randomized Controlled Trial Study Protocol
Version 1.0 – 2 May 2023, Amendment 1 dated 26 June 2023

Protocol Activity	Baseline (study commencement)	Week 1	Week 4	Week 8	Week 12 (intervention end)	Week 16 (last data collection)	Will be done by
Feasibility	x	x	x	x	x	x	RC
Medication adherence rate (medication refill adherence-MRA)						x	Pharmacy & RC
Self-report adherence (ASK-12)		x			x		Pts & RC
Side effects monitoring	x	x	x	x	x		Pts & RC
Toxicity self-management (PAM-SF)		x			x		Pts & RC
Anxiety, depression and symptoms (PROMIS)		x			x		Pts & RC
Quality of life (FACT-G)		x			x		Pts & RC
Optimal intervention strategy					x		RC

Note: MI: motivational interviewing, Nurs: nurses, Pharm: pharmacists, Pts: participants, RC: research coordinator

Pilot Randomized Controlled Trial Study Protocol
Version 1.0 – 2 May 2023, Amendment 1 dated 26 June 2023

4 List of study documents

Attachment number	Document title	Purpose
1	Participant Information and Consent Form	Provide a detailed summary of the study and participant requirements. Obtain participant's consent to participate in the study. The last section is used for participants to request withdrawal from the study
2	Survey booklet	Obtain participant's information and feedback, including: 
 - demographic information - status of anxiety, depression and other symptoms - quality of life - knowledge, skills and confidence in condition and symptom self-management - barriers to MA and adherence-related behaviour - acceptability and intention to use SAMSON
3a	SAMSON app and website user manual – for patients	Provide information on how to install and use the SAMSON mobile app and website
3b	SAMSON website user manual – for health professionals	Provide information on how to use the SAMSON web page
4a	Intervention manual – for pharmacists	Provide brief information on the study and protocol for pharmacists involving in the intervention to deliver consultations
4b	Intervention manual – for nurses	Provide brief information on the study and protocol for nurses involving in the intervention to deliver consultations
5	Participant spreadsheets	Obtain participants' contact information
6	Recruitment flyer	Provide brief information to patients about the study
	Appendix 1	Medicine information provided in the SAMSON app
	Appendix 2	Self-care advice on common drug side effects
	Appendix 3	Examples of side effects information and self-care advice in the SAMSON app

5 Background information and study rationale

5.1. Medication non-adherence and its burden

Medication Adherence (MA) is defined as "the extent to which a person's behaviour- taking medication, following a diet, and/or executing lifestyle changes, corresponds with agreed recommendations from a health care provider" (Sabate, 2003b, p. 3). Research has consistently shown adherence rates are typically lower among patients with chronic conditions (about 50% in developed countries and much lower in developing countries), as compared to those with acute conditions (Carter et al., 2003; Col et al., 1990; Cramer et al., 2003; Haynes et al., 2002; Sabate, 2003a; World Health Organization, 2003). Among patients with cancers, this rate varies between 16 to 100% (Bouwman et al., 2017) and often worsens overtime (Hershman et al., 2009). There is no single standard threshold for acceptable adherence, however, patients can be considered as suboptimal-adherent if their adherence rate is less than 80% (Banning, 2012; Geynisman & Wickersham, 2013; Spoelstra & Given, 2011).

Suboptimal medication adherence is often associated with poorer health outcomes and increased healthcare costs (Col et al., 1990; Kane & Shaya, 2008). Studies have shown that poor adherence to prescribed regimens can significantly impact survival rates (Makubate et al., 2013), and result in patients' disease progression, reduced functional ability, increased risk of hospitalisation, and lower quality of life (Col et al., 1990; Fuso et al., 1995; Garcia-Aymerich et al., 2000). Annually, in Australia, it is estimated that 250,000 Australians experience medication-related hospital admissions, which costs Australian taxpayers \$1.4 billion (Lim et al., 2019). MA and error management are essential for tackling chronic conditions effectively and play critical roles in improving healthcare today (Sabate, 2003a).

5.2. Medication adherence interventions

Despite the problem of non-adherence being discussed, it is not consistently part of routine care, and efforts to address the problem have been fragmented (Sabate, 2003a). According to the results from our recently published systematic review, single strategies to promote adherence (e.g. education, reminders, or monitoring) are not sufficient to improve adherence (Dang et al., 2022). Multi-component interventions that involve collective adherence strategies (patient education, reminders, self-monitoring, reinforcement, and supportive counselling), especially if they were tailored to patients, were most effective to improve adherence to oral anti-cancer medicines (Dang et al., 2022).

Furthermore, the review revealed that digital solutions can enhance multi-component interventions effectively and efficiently (Dang et al., 2022; Gambalunga et al., 2020; Odeh et al., 2015), given the already-scarce resources in the health system (Phanareth et al., 2017). With the digital boom, technological advances, such as smartphones with powerful capabilities and features, have become one of the most important innovations in healthcare as they provide many advantages, including improving clinical outcomes and cost efficiency, and increased acceptability by patients (Gambalunga et al., 2020; World Health Organization, 2011). These technologies have been increasingly used to assist treatment management through enabling therapeutic education and monitoring of patient self-management (Hamine et al., 2015). Results from a systematic review of 188 studies on mobile health applications have shown that digital technology is appropriate and helpful in increasing treatment adherence (Perez-Jover et al., 2019).

5.3. SAMSON intervention solution

Harnessing the potential of technologies, we developed SAMSON - a novel patient-centred, comprehensive digital solution to improve MA in cancer. The solution comprises two components:

Pilot Randomized Controlled Trial Study Protocol
Version 1.0 – 2 May 2023, Amendment 1 dated 26 June 2023

- 1) SAMSON mobile app involving individually tailored smartphone alerts and real-time advice for side-effect self-management. The beta-version of SAMSON mobile app was tested by 30 people with haematological cancer at Peter Mac in 2021 (HREC/74134/PMCC).
- 2) Health professional tele-consultations, using MI skills being trained via the MITP to promote patient's adherence and side-effect self-management. The MITP is a digital training platform, which was created to provide general training on motivational interviewing, communication skills with focus on medication adherence aspects for oncology clinicians. The MITP was co-designed with healthcare professionals, stakeholders and consumer representatives, and developed in 2022. It is available on Peter Mac's learning management system and being tested by healthcare professionals at the hospital. The data collection is expected to complete in March 2023 the latest.

Pilot Randomized Controlled Trial Study Protocol
Version 1.0 – 2 May 2023, Amendment 1 dated 26 June 2023

6 Objectives

The objective of this work is to evaluate the acceptability, feasibility (recruitment, randomisation, retention, intervention adherence and assessment processes) and potential efficacy of the SAMSON intervention solution among 30 to 50 patients with haematological, lung or melanoma cancer newly administered oral anti-cancer medicines.

7 Methods

7.1. Study design

This is a pilot two-arm RCT.

After completion of baseline questionnaires, participants will be remotely randomised to either intervention or control groups (1:1 ratio), using a computer-generated randomisation chart. Participants of the intervention group will receive the SAMSON intervention solution, while those in the control group will receive usual care, for 12 weeks immediately following the randomisation.

Primary outcomes:

- Intervention group: acceptability will be assessed at week 12.
- Both groups: Feasibility will be assessed throughout the study.

Secondary outcomes: adherence will be assessed at week 16. side-effect monitoring; toxicity self-management; anxiety, depression and symptoms; quality of life will be assessed at weeks 1 and 12; and optimal intervention strategy will be assessed at week 12.

Data collection and results reporting will be in line with the Consolidated Standards of Reporting Trials (CONSORT) criteria for pilot RCTs (Schulz et al., 2010).

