7.2. Number of participants and study duration

Thirty to fifty patients will be recruited into the pilot RCT. The study will run for 16 weeks. During this 16-week, the patient in the intervention arm will:

- have access to the SAMSON mobile app (the first component of the intervention solution) throughout the study period, and
- receive initial pharmacist consultation and tele-consultations provided by their care team at Peter Mac, i.e nurses or pharmacists, in weeks 1, 4, 8 and 12.

All randomisations will be done by the study statistician.

Recruitment will be undertaken over a period of 6 months and the intervention is expected to be completed in ten months from recruitment commencement.

The patient in the controlled arm will receive usual care at the hospital (see details in section 7.9.2).

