7.6. Study population

7.6.1. Inclusion criteria

All the following criteria must be satisfied for enrolment in the study.

- 1) A confirmed diagnosis of any-stage haematological, lung or melanoma cancer;
- 2) Scheduled to commence oral anti-cancer medicine(s) as part of routine care or commencing treatment/currently treated with the medication for less than 12 months;
- 3) Willing to have oral anti-cancer medicine(s) dispensed at Peter Mac;
- 4) Over 18 years old;
- 5) Proficient in English; and
- 6) Accessibility to the internet, a smartphone (and computer), and/or telehealth.

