7.7.2. Secondary outcomes

7.7.2.1. *Medication adherence* will be assessed by medication refill adherence (MRA) (Hess et al., 2006) in week 16. A systematic review of current or recently used measures of calculating adherence from administrative data recommended MRA as the preferred measure of adherence, because of its convenience while still produces equivalent results comparing with other measures (Hess et al., 2006). Pharmacy dispensing data (Merlin) will be used to determine MRA, defined as the total days' supply divided by the number of days of study participation and multiplied by 100. Data will be extracted at a single time point once the last patient has reached week 16. Data will be extracted by pharmacy as part of collaboration in this research program. Note that the total days' supply will include any deliberate break periods, e.g. if the patient is asked to take the drug for 21 days, follows by 7 days break, then the total days' supply will be 28. If the patient needs to reduce the dose for some medical reasons, e.g. side effects, the MRA formulation will be manually adjusted accordingly. In this study, the patient will be considered as optimal adherence if their MRA is $\geq 90\%$.

Note that MRA may be impacted if patients are given larger pack sizes and therefore not coming in at every cycle or if dose adjustments occur due to toxicity resulting in a participant using a single pack for longer. Therefore, the RC will collect this information and compare the MRA with patients' responses to drug reminders on the SAMSON mobile app and discuss with the PI case by case.

7.7.2.2. *Self-report adherence* will be measured by ASK-12 (Matza et al., 2009) at weeks 1 and 12. This instrument was originally designed with 20 questions to provide a practical, yet detailed, assessment of adherence behaviour as well as potential barriers to adherence (Hahn et al., 2008). The ASK-20 has been used in studies focusing on a range of treatments and settings, for example asthma and different pharmacy programs. The shorter refined version of this instrument, i.e. ASK-12 includes 12 items in three sub-scales: adherence behaviour, health beliefs and inconvenience or forgetfulness. The tool has good internal consistency reliability (Cronbach alpha = 0.75) and test-retest reliability (intraclass correlation = 0.79). This tool was found to be practical and useful for the

Pilot Randomized Controlled Trial Study Protocol

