- 2) Health professional tele-consultations, using MI skills being trained via the MITP to promote patient's adherence and side-effect self-management by:
 - Medication reconciliation,
 - MA education,
 - Medication administration, missed dose and side-effect education, including side-effect management strategies,
 - Assessment of barriers and concerns
 - Addressing barriers and concerns

MITP is a digital training platform, which was created to provide general training on MI, communication skills with focus on MA aspects for oncology clinicians. The MITP consists of different eLearning adaptive, interactive and possibly personalised modules, including formative assessments, being provided online via Peter Mac's learning management system (LMS) (Learning Hub). The MITP was developed in 2022 and is being trialled by oncology clinicians at Peter Mac. After the study's completion, expected in March 2023, the MITP will be refined accordingly, and will then be delivered in conjunction with the refined SAMSON mobile app as the SAMSON intervention solution in this study.

The structured counselling sessions will be either in person or online at baseline, week 1, 4, 8 and 12. The quantity and length of consultations will be tailored to patient's need and adherence status, assessed by the consultant. The initial consultation will be delivered in person or online by a pharmacist when patients receive their medicines. The tele-counselling sessions will be delivered via phone or telehealth by clinical nurses or pharmacists of participating departments at Peter Mac. In departments where there is no allocated clinical pharmacist, nurses will deliver teleconsultations or an alternative approach will be arranged in discussion between the patient's care team.

Nurses and pharmacists will participate in the study depending on their availability and interest. They will need to have at least one year of clinical experience in providing oncology care and successfully complete the MITP training to conduct the structured counseling sessions with participants. Study nurses and pharmacists will be provided instruction manuals to guide them for each consultation. It is predicted that some nurses and pharmacists involved in the MITP testing study in 2022 will

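### A late treatment start alone can put a fully adherent new starter below the 90% MRA rule, because the denominator includes days before the first supply

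*Protocol*

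**What the plan says.** Section 7.6.1, criterion 2, admits patients on either side of treatment start: "Scheduled to commence oral anti-cancer medicine(s) as part of routine care or commencing treatment/currently treated with the medication for less than 12 months". It sets no maximum wait before the first supply.

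Section 7.1 starts the intervention or usual-care period from allocation. The intervention group receives SAMSON, "while those in the control group will receive usual care, for 12 weeks immediately following the randomisation". Section 7.5 has the statistician randomise once consent is given. Neither section waits for the medicine.

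Section 7.7.2.1 gives medication refill adherence (MRA) as "defined as the total days' supply divided by the number of days of study participation and multiplied by 100". On the cut-off it says "the patient will be considered as optimal adherence if their MRA is" 90% or more. It corrects for deliberate breaks and for medically required dose reductions. Larger packs and toxicity-related dose adjustments go to case-by-case discussion. A delayed start is not mentioned, nor is supply that runs past week 16.

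Section 7.2 sets the length: "The study will run for 16 weeks".

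The schedule of assessments puts the initial consultation at baseline and the first teleconsultation at week 1. Section 7.8 ties the initial consultation to the drug: "The initial consultation will be delivered in person or online by a pharmacist when patients receive their medicines".

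**The concern.** For a patient who is only scheduled to start, study time and treatment time begin on different dates, and the protocol counts from study entry or randomisation. Days before the first supply add to the MRA denominator and nothing to the numerator. Someone who never misses a dose can then be recorded as less than optimally adherent.

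The same gap exposes a conflict in the intervention timetable. The baseline consultation in the schedule and the consultation at receipt of medicines in section 7.8 are the same event only if dispensing coincides with baseline. Nothing requires that.

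The stated objective names newly treated patients, so starters are central to the trial. Section 7.10 says the results will inform endpoint selection and sample size for the larger RCT. An adherence rate that partly measures booking delays is a poor basis for either.

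**Working it through.** The protocol states no MRA figure, so there is nothing to reproduce. The check applies its own formula to a patient who takes every dose.

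**Inputs from the protocol**
- Participation: 16 weeks = 112 days (section 7.2).
- Intervention period: 12 weeks = 84 days from randomisation (section 7.1).
- Cut-off: MRA of at least 90% (section 7.7.2.1).
- Sample: 30 to 50 patients at 1:1, so 15 to 25 per arm.

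**Assumptions**
- First supply comes d days after study entry, with entry and randomisation taken as the same day.
- Packs hold 28 or 30 days and are refilled exactly on time.

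The protocol gives no value for d or for pack size.

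**Reading A: supply cut off at day 112.** MRA = 100 × (112 − d)/112. This falls below 90% when d > 0.10 × 112 = 11.2, so from d = 12.

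**Reading B: whole packs counted as dispensed.** Number of packs = (112 − d)/pack size, rounded up. MRA = 100 × packs × pack size/112.
- 30-day packs: at d = 21, 91/30 rounds up to 4, giving 120/112 = 107.1%. At d = 22, 90/30 = 3, giving 90/112 = 80.4%.
- 28-day packs: at d = 27, 85/28 rounds up to 4, giving 112/112 = 100%. At d = 28, 84/28 = 3, giving 84/112 = 75.0%.

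| Delay d (days) | A: cut at day 112 | B: 28-day packs | B: 30-day packs | Weeks on drug within the 12 |
|---|---|---|---|---|
| 0 | 100.0% | 100.0% | 107.1% | 12.0 |
| 7 | 93.8% | 100.0% | 107.1% | 11.0 |
| 11 | 90.2% | 100.0% | 107.1% | 10.4 |
| 12 | 89.3% | 100.0% | 107.1% | 10.3 |
| 14 | 87.5% | 100.0% | 107.1% | 10.0 |
| 22 | 80.4% | 100.0% | 80.4% | 8.9 |
| 28 | 75.0% | 75.0% | 80.4% | 8.0 |

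The last column is 12 − d/7.

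**Sensitivity to window length.** If participation were taken as 84 days, Reading A would cross the cut-off at d = 9 (75/84 = 89.3%).

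**Effect on an arm's rate.** One misclassified patient moves the proportion with optimal adherence by 1/25 = 4.0 to 1/15 = 6.7 percentage points.

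**With the window begun at first supply.** Supply inside the window is 112 − d days over a denominator of 112 − d days, so MRA is 100% for any d.

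**The case against.** **The gap may be short.** Read together, the schedule and section 7.8 suggest that baseline and dispensing are meant to be close in the intervention arm. Many participants may already be on treatment, since section 7.6.1 allows up to 12 months of prior use and section 7.4.1 recruits partly from dispensing records. This stands as a limit on how often the problem arises. It does not remove it: no passage caps the wait, and the link to dispensing is not stated for study entry in the control arm.

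**Not every day before the start counts as non-adherence.** A reader might infer that each such day lowers MRA. That holds only if supply is cut off at week 16, which the protocol does not say. On the literal formula with 28-day packs, delays of up to 27 days cost nothing.

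**The loss of intervention is not simply 12 weeks minus the delay.** Section 7.2 gives app access throughout the 16 weeks, so a 14-day delay still leaves 14 weeks of access on drug. The initial consultation also covers future barriers, so contact before the first dose is not plainly wasted. What remains is that the teleconsultations are fixed at weeks 1, 4, 8 and 12 whatever the start date.

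**The first ASK-12 is not a further defect.** A reader might object that it could precede any dose. Section 7.5 has it completed within three days of consent, before participants learn their arm, so it serves as a baseline.

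**Both arms follow the same rule.** Under randomisation no between-arm bias is expected unless delays differ by arm. MRA is secondary, and the analysis is mainly descriptive. Both points stand and limit the consequence to misclassification and noise.

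**Conclusion.** The point holds as a defect in the written MRA rule. With no cap on the wait and no correction for a late start, a fully adherent starter can be classed below 90% through scheduling alone. The delay needed is 12 days with supply cut off at day 112, 22 days with whole 30-day packs and 28 days with whole 28-day packs. These thresholds assume a 112-day window from entry and perfect refilling. The protocol does not say which counting method applies, so the size of the error is undetermined, and the number of patients affected cannot be estimated from the document.

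The harm is to the adherence rates carried forward to the larger trial. The documents do not show a biased comparison between arms or a threat to the feasibility thresholds. Separately, sections 7.1 and 7.8 leave open when the 12 weeks and the initial consultation begin for patients who have not started.

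**What to change.** **Section 7.7.2.1.** For patients who have not started at study entry, begin the MRA denominator in both arms at the first dispensing on or after entry. Count only supply covering days inside the window to week 16. For current users, say whether stock held at entry counts. If it does not, cutting supply at week 16 gives them the same apparent deficit: 14 days in hand gives (112 − 14)/112 = 87.5%.

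**Reporting.** Give the delay from randomisation to first dispensing by arm, and the number who never received a supply, for whom this MRA is undefined. The report by arm is needed because the window would begin at an event after randomisation.

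**Sections 7.1 and 7.8.** Reconcile them on when the 12 weeks and the initial consultation begin for patients not yet started. The timing is for the investigators to settle. One option is to time allocation close to first dispensing, which fixes the window before the arm is known. Its downsides are later randomisation and some consented patients never being randomised. Because section 7.7.1.2 defines retention over all who consent, those patients would also lower a primary feasibility measure. The MRA correction does not depend on this option.

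**Cost.** A short amendment. Pharmacy already extracts the dispensing data, so no new data collection is needed. Starters would have a somewhat shorter MRA window than 112 days.
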